5.6.3 Vital Signs

Descriptive statistics for vital signs parameters (ie, diastolic and systolic BP, pulse, respiration rate, temperature) and weight, and changes from Baseline will be presented by treatment group and day relative to dosing, separately for each cohort.

Vital sign values will be listed. Clinically notable vital sign values will be identified on the listings as those above (H) or below (L) a clinically notable range (Table 1). Categorical analyses of subjects (number and percent) who fall outside the below clinically notable vital sign ranges will also be presented by treatment group and visit.

Table 1 Vital Sign Criteria

Variable	Criterion value ^a	Change relative to baseline ^a	Clinically notable range
Heart rate	>120 bpm	Increase of ≥ 15 bpm	H
	<50 bpm	Decrease of ≥ 15 bpm	L
Systolic BP	>180 mmHg	Increase of ≥ 20 mmHg	H
	<90 mmHg	Decrease of ≥ 20 mmHg	L
Diastolic BP	>105 mmHg	Increase of ≥ 15 mmHg	H
	<50 mmHg	Decrease of ≥ 15 mmHg	L

BP = blood pressure, bpm = beats per minute, H = high, L = low.

- a. Clinically notable means that a value must meet the criterion value and must attain the specified magnitude of change relative to baseline.

5.6.4 Electrocardiograms

Descriptive statistics for ECG parameters and changes from Baseline will be presented separately for each cohort. Shift tables will present changes from Baseline in ECG interpretation (categorized as normal; abnormal, not clinically significant; and abnormal, clinically significant) by time point.

For each subject, the maximum observed corrected QT interval calculated using Fridericia's formula (QTcF), and the maximum prolongation from baseline in QTcF will be compiled. Categorical analyses of subjects (number and percent) with maximum observed QTcF values >450 msec, >480 msec, and >500 msec and maximum prolongations (from Baseline) in QTcF >30 msec and >60 msec will be presented by treatment group and by time point. Categorical analyses of subjects (number and percent) with maximum observed PR values >220 msec, and QRS values > 120 msec will be presented by treatment group and by time point.

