9.5.1.5.3 LABORATORY MEASUREMENTS

Clinical laboratory tests to be performed, including hematology, chemistry, and urinalysis, are summarized in Table 4. Subjects should be in a seated or supine position during blood collection. The Schedule of Procedures/Assessments (Table 5 and Table 6) shows the visits and time points at which blood for clinical laboratory tests and urine for urinalysis will be collected in the study.

Table 4 List of Laboratory Tests

Category	Parameters
Hematology	Hematocrit, hemoglobin, platelets, RBC count, and WBC count with differential (bands, basophils, eosinophils, lymphocytes, monocytes, neutrophils)
Chemistry	
Electrolytes	Chloride, potassium, sodium, calcium
Liver function tests	Alanine aminotransferase, alkaline phosphatase, aspartate aminotransferase, gamma glutamyl transpeptidase, direct bilirubin, total bilirubin
Renal function tests	Blood urea/blood urea nitrogen, creatinine
Other	Total protein, albumin, globulin, cholesterol, triglycerides, glucose, lactate dehydrogenase, uric acid
Urinalysis	Bacteria, casts, crystals, epithelial cells, glucose, ketones, occult blood, pH, protein, RBCs, specific gravity, WBCs

CYP3A = cytochrome P450 Family 3A, RBC = red blood cell, WBC = white blood cell.

Clinical laboratory tests during the study will be performed by PPD Clinical Laboratories. All blood and urine samples will be collected and sent to the central laboratory on the day of collection unless otherwise instructed. In cases of a safety concern, blood samples may be split (or 2 samples drawn) to allow a local laboratory analysis in addition to the central

laboratory: A central laboratory will perform tests to qualify subjects for entry into the study. Laboratory certification as available will be included in the final clinical study report for this study.

A laboratory abnormality may meet the criteria to qualify as an AE as described in this protocol (see [Section 9.5.1.5.1](#)) and the CRF Completion Guidelines. In these instances, the AE corresponding to the laboratory abnormality will be recorded on the Adverse Event CRF.

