9.5.1.5.6 ELECTROCARDIOGRAMS

Twelve-lead electrocardiograms will be obtained and reviewed locally as designated in the Schedule of Procedures/Assessments ([Table 5](#) and [Table 6](#)).

An ECG abnormality may meet the criteria of an AE as described in this protocol (see [Section 9.5.1.5.1](#)) and the CRF Completion Guidelines. In these instances, the AE corresponding to the ECG abnormality will be recorded on the Adverse Events CRF.

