9.7.1.8.3 LABORATORY VALUES

Laboratory results will be summarized using Système International (SI) units, as appropriate. For all quantitative parameters listed in [Section 9.5.1.5.3](#), the actual value and the change from baseline to each postbaseline visit and to the end of treatment (defined as the last on-treatment value) will be summarized by visit and treatment using descriptive statistics. Qualitative parameters listed in [Section 9.5.1.5.3](#) will be summarized using frequencies (number and percentage of subjects), and changes from baseline to each postbaseline visit and to end of treatment will be reported using shift tables. Percentages will be based on the number of subjects with both nonmissing baseline and relevant postbaseline results.

Laboratory test results will be assigned a low/normal/high (LNH) classification according to whether the value was below (L), within (N), or above (H) the laboratory parameter's reference range. Within-treatment comparisons for each laboratory parameter will be based on 3-by-3 tables (shift tables) that compare the baseline LNH classification to the LNH classification at each postbaseline visit and at the end of treatment. Similar shift tables will also compare the baseline LNH classification to the LNH classification for the highest and lowest value during the treatment period.

[Appendix 1](#) (Sponsor's Grading for Laboratory Values) presents the criteria that will be used to identify subjects with treatment-emergent markedly abnormal laboratory values (TEMAV). Except for phosphate, a TEMAV is defined as a postbaseline value with an increase from baseline to a grade of 2 or higher. For phosphate, a TEMAV was defined as a postbaseline value with an increase from baseline to a grade of 3 or higher. When displaying the incidence of TEMAVs, each subject may be counted once in the laboratory parameter high and in the laboratory parameter low categories, as applicable.

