5.6 Safety Analyses

Safety analyses will be performed on the Safety Analysis Set unless otherwise specified. Safety data, presented by treatment group, will be summarized on an “as treated” basis using descriptive statistics (eg, n, mean, standard deviation, median, minimum, maximum for continuous variables; n [%] for categorical variables). Safety variables include treatment-emergent adverse events (TEAEs), clinical laboratory parameters, vital signs and 12-lead ECG results. Baseline for all safety analyses is defined as the last predose assessment prior to each periods’ dosing. Extent of Exposure

The extent of exposure (mean daily dose, cumulative dose, duration of exposure) to study drug will be summarized descriptively for lemborexant in the OSA Cohort. For the HV Cohort extent of exposure will be summarized by the number of subjects receiving each treatment.

Compliance for the OSA Cohort for lemborexant will be calculated on the basis of the number of tablets dispensed, lost, and returned, separately for each type (dose) of tablet. Summaries will provide descriptive summary statistics and number (percentage) of subjects below 80%, between 80% and 120%, and greater than 120%.

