5.6.2 Laboratory Values

Clinical laboratory values will be evaluated for each laboratory parameter by subject separately for each cohort. Abnormal laboratory values will be identified as those outside (above or below) the normal range. Reference (normal) ranges for laboratory parameters will be included in the clinical study report for this study. Descriptive summary statistics (eg, mean, SD, median, minimum, maximum for continuous variables, and number and percentage for categorical variables) for the laboratory parameters and changes from baseline will be evaluated by treatment group and visit.

Laboratory test results will be assigned a low-normal-high (LNH) classification according to whether the value was below (L), within (N), or above (H) the laboratory parameter's reference range. Within-treatment comparisons will be based on 3 by 3 tables (shift tables) that, for a particular laboratory test, compare the Study Baseline LNH classification to the LNH classification at end of study/early termination, by treatment group.

Clinical laboratory results postbaseline will be evaluated for markedly abnormal values. A laboratory test will be considered markedly abnormal if the result worsens to meet Eisai grading criteria for laboratory values limit of Grade 2 or higher. If the Grade 2 limit is missing, the Grade 1 limit will be considered. [Appendix 13.1](#) presents the Eisai grading criteria for laboratory values that were used to identify subjects with markedly abnormal laboratory values. For the incidence of markedly abnormal laboratory values, each subject may be counted once in the laboratory parameter value high and in the laboratory parameter low categories as applicable.

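### The SAP tabulates labs and ECG categories by treatment, but a completer's only scheduled post-dose lab set and 12-lead ECG come at end of study, after all crossover treatments

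*SAP*

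**What the plan says.** **The analysis plan.** SAP 5.6 sets a general rule: "Safety data, presented by treatment group, will be summarized on an" as-treated basis, with labs and 12-lead ECG among the variables covered. It also defines baseline for all safety analyses separately for each period, as the last assessment before that period's dosing.

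SAP 5.6.2 adds that lab "changes from baseline will be evaluated by treatment group and visit", and that the shift tables "compare the Study Baseline LNH classification to the LNH classification at end of study/early termination, by treatment group". Its sentence on markedly abnormal labs names no treatment split, so only the general rule reaches that table.

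In SAP 5.6.4, "maximum prolongations (from Baseline) in QTcF >30 msec and >60 msec will be presented by treatment group and by time point". The QTcF, PR and QRS category tables all carry this split. The ECG descriptive statistics are per cohort and the ECG shift tables by time point.

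Protocol 9.7.1.8.3 goes further for labs. Change from baseline to each visit and "to the end of treatment (defined as the last on-treatment value) will be summarized by visit and treatment". It also asks for shift tables against the "LNH classification for the highest and lowest value during the treatment period".

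**The schedule.** Protocol 9.5.1.5.3 says the schedule (Tables 5 and 6) "shows the visits and time points at which blood for clinical laboratory tests and urine for urinalysis will be collected". Protocol 9.5.1.5.6 does the same for ECGs: "Twelve-lead electrocardiograms will be obtained and reviewed locally as designated in the" schedule. Both tables mark labs and 12-lead ECG at Visit 1, Visit 3A, EOS/ET and Unscheduled, and nowhere else.

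SAP section 7 records no change from the protocol's planned analyses. SAP sections 9 and 11 place derivation rules and table shells in separate documents.

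**The concern.** In a crossover, a by-treatment safety table is useful when each treatment has its own post-dose values. Here a completer's only scheduled post-dose lab set and ECG come after two treatments (OSA) or three (HV). Nothing in the protocol or SAP says which treatment that value belongs to.

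Safety and tolerability is a stated secondary objective in both cohorts. A QTcF table with lemborexant and placebo columns invites the reader to think that ECGs taken on drug were compared with ECGs taken on placebo. For completers' scheduled data that comparison does not exist. A reassuring table would say nothing about acute on-drug effects, and an abnormal value could appear under a treatment the subject was not taking when it was recorded.

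**Working it through.** The plan gives no figure to reproduce, so the check is a count of schedule marks and days.

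**Inputs (protocol Tables 5 and 6 and their footnotes)**

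| Cohort | Visits with lab and ECG marks | Last dose of each period (nominal day) | EOS (nominal day) | Planned completers |
|---|---|---|---|---|
| HV | 1, 3A, 6 (EOS/ET), Unscheduled | 1, 16, 31 | 46 | 12 |
| OSA | 1, 3A, 9 (EOS/ET), Unscheduled | 8, 30 | 45 | 30 |

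Visit 3A is predose: footnote m of Table 5 and footnote n of Table 6 put dosing after all baseline assessments. EOS is 14 to 21 days after the final dose (footnotes e and f). Washout is 14 to 21 days after the discharge visit (footnote d in both tables).

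**1. Post-dose values per completer.** After Visit 3A, the only scheduled mark is EOS. That is 1 lab set and 1 ECG in each cohort.

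**2. Values within a treatment period after dosing.** HV has 12 × 3 = 36 periods and OSA has 30 × 2 = 60, so 96 periods in 12 + 30 = 42 completers. Scheduled labs or ECGs in them after dosing: 0.

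**3. Baseline.** No lab or ECG is marked before Period 2 or 3 dosing (HV Visits 4A and 5A, OSA Visit 6A). The per-period baseline of SAP 5.6 therefore has no new scheduled value after Period 1.

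**4. Maximum values.** With one scheduled post-dose ECG, a completer's maximum QTcF and maximum prolongation are simply the EOS value and its change.

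**5. What a treatment column would contain.** Suppose EOS is assigned to the last treatment received. This is an assumption, since the documents state no rule. The placebo column would then hold completers of OSA sequence E and HV sequence B, all previously given lemborexant. Days from last lemborexant dose to EOS:

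- OSA E, nominal: 45 − 8 = 37. Limits: 15 to 22 days from last Period 1 dose to first Period 2 dose (washout runs from the morning after dosing), plus 7 days to the last Period 2 dose, plus 14 to 21 days to EOS. This gives 15 + 7 + 14 = 36 to 22 + 7 + 21 = 50.
- HV B, nominal: 46 − 16 = 30. Limits: 15 + 14 = 29 to 22 + 21 = 43.
- Sequences ending on lemborexant, nominal: OSA D 45 − 30 = 15; HV A and C 46 − 31 = 15. Limits 14 to 21.

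The OSA placebo column would be 30 / 2 = 15 completers if the 1:1 ratio holds exactly. No HV allocation ratio is stated; equal allocation, if assumed, gives 12 / 3 = 4.

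A different assumption, entering EOS under every treatment received, makes the completers' columns identical and every difference 0.

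**6. Contrast with vital signs.** These are marked in every period (HV Visits 3B, 4A, 4B, 5A and 5B; OSA Visits 3B, 5A, 5B, 6A, 6B, 8A and 8B). By-treatment presentation works for them, so the mismatch is specific to labs and 12-lead ECG.

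**The case against.** **Attribution may be settled elsewhere.** Table shells and derivation rules were not available, and the as-treated basis with a per-period baseline points naturally to the last treatment. It would be wrong to infer that no attribution rule exists. But an as-treated rule settles planned versus actual treatment, and no rule can turn an EOS value into an on-treatment one.

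**The OSA text could be read as scheduling Day 8 labs and ECG.** Protocol 9.1.2.2.1 says Day 8 repeats the Day 1 procedures. The tests it then lists (pregnancy, drug and alcohol) are examples rather than a full list, and it adds routine safety assessments. Those assessments are, however, tied to the schedule, and Table 6 marks no lab or ECG at Visits 5A, 5B, 8A or 8B.

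**Readers would see these are EOS values.** The tables are also split by visit or time point, and the SAP lab shift table already runs from Study Baseline to end of study or early termination. That stands, and for the shift table only the treatment split is at issue.

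**The gain is mostly a label.** For completers, a by-sequence table holds the same subjects as a last-treatment table. True. What changes is that the treatment label goes, an overall column is added and the limitation is stated.

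**ET and unscheduled values exist.** They do, and some may be attributable to a treatment. The point covers completers' scheduled values only.

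A reader might also infer that the trial collects no on-treatment safety data, or that EOS labs and ECGs are worthless. Neither is supported. Adverse events and vital signs are collected in every period, and an effect that persisted to EOS could still appear.

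**Conclusion.** The point holds for completers' scheduled labs and 12-lead ECGs. Each completer has one post-dose lab set and one post-dose ECG, both at EOS, and 0 of 96 treatment periods contain a scheduled value after dosing. The by-treatment lab summaries and shift tables of SAP 5.6.2 and the category tables of SAP 5.6.4 therefore cannot compare on-drug with placebo in these data. The end-of-treatment and highest/lowest lab outputs of protocol 9.7.1.8.3 cannot be filled from them either.

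The count rests only on Tables 5 and 6. The 37- and 30-day figures also assume assignment to the last treatment and nominal visit days.

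It would be too strong to say that the trial's conclusions are at risk: no primary endpoint or decision rule uses these tables. The harm is to safety reporting, through a treatment label on values not taken on that treatment. It should be corrected before the SAP is finalised.

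**What to change.** 1. **SAP 5.6.2 and the category tables of 5.6.4:** present labs and ECG per cohort as Day 1 study baseline to EOS/ET, overall, without treatment columns. Columns by sequence may be added if labelled as sequence. Treat the markedly abnormal lab incidence the same way.
2. **SAP 5.6:** make labs and 12-lead ECG explicit exceptions to the by-treatment rule and to the per-period baseline.
3. **ET and unscheduled values:** keep them in the summaries, and list them with the last treatment received and days since last dose.
4. **Limitation:** state that no on-treatment labs or 12-lead ECGs were scheduled.
5. **SAP section 7:** replace the present entry with the departures from protocol 9.7.1.8.3, namely no by-treatment lab split, no end-of-treatment summaries or shift tables, and no highest/lowest-value shift tables. The SAP already leaves out the last two groups without saying so.

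The cost is wording in SAP 5.6, 5.6.2, 5.6.4 and section 7, plus the affected table shells. It adds no procedures and needs no protocol amendment.

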6 INTERIM ANALYSES

No interim analyses are planned for this study.

7 CHANGES IN THE PLANNED ANALYSES

Not applicable.

8 DEFINITIONS AND CONVENTIONS FOR DATA HANDLING

No missing data will be imputed.

9 PROGRAMMING SPECIFICATIONS

All analysis will be done separately for each cohort.

All pharmacodynamic and safety data will be presented using nominal timepoint as reported in the data. No additional derivation will be performed for analysis visit window.

The rules for programming derivations and dataset specifications are provided in separate documents.

10 STATISTICAL SOFTWARE

All statistical analyses will be performed using SAS v 9.3 or later.

11 MOCK TABLES, LISTINGS, AND GRAPHS

The study table, listing, and graph (TLG) shells will be provided in a separate document, which will show the content and format of all tables, listings, and graphs in detail. There will be two separate independent TLGs for the two cohorts.

13 APPENDICES

13.1 Sponsor's Grading for Determining Markedly Abnormal Laboratory Results

The following table of Sponsor's Grading for Laboratory Values is copied from the [protocol, Appendix 1](#).

Sponsor's Grading for Laboratory Values

	Grade 1	Grade 2	Grade 3	Grade 4
BLOOD/BONE MARROW				
Hemoglobin	<LLN – 10.0 g/dL <LLN – 100 g/L <LLN – 6.2 mmol/L	<10.0 – 8.0 g/dL <100 – 80 g/L <6.2 – 4.9 mmol/L	<8.0 g/dL <80 g/L <4.9 mmol/L; transfusion indicated	life-threatening consequences; urgent intervention indicated
Leukocytes (total WBC)	<LLN – $3.0 \times 10^9/L$ <LLN – 3000/mm ³	<3.0 – $2.0 \times 10^9/L$ <3000 – 2000/mm ³	<2.0 – $1.0 \times 10^9/L$ <2000 – 1000/mm ³	< $1.0 \times 10^9/L$ <1000/mm ³
Lymphocytes	<LLN – 800/mm ³ <LLN – $0.8 \times 10^9/L$	<800 – 500/mm ³ <0.8 – $0.5 \times 10^9/L$	<500 – 200/mm ³ <0.5 – $0.2 \times 10^9/L$	<200/mm ³ < $0.2 \times 10^9/L$
Neutrophils	<LLN – $1.5 \times 10^9/L$ <LLN – 1500/mm ³	<1.5 – $1.0 \times 10^9/L$ <1500 – 1000/mm ³	<1.0 – $0.5 \times 10^9/L$ <1000 – 500/mm ³	< $0.5 \times 10^9/L$ <500/mm ³
Platelets	<LLN – $75.0 \times 10^9/L$ <LLN – 75,000/mm ³	<75.0 – $50.0 \times 10^9/L$ <75,000 – 50,000/mm ³	<50.0 – $25.0 \times 10^9/L$ <50,000 – 25,000/mm ³	< $25.0 \times 10^9/L$ <25,000/mm ³
METABOLIC/LABORATORY				
Albumin, serum-low (hypoalbuminemia)	<LLN – 3 g/dL <LLN – 30 g/L	<3 – 2 g/dL <30 – 20 g/L	<2 g/dL <20 g/L	life-threatening consequences; urgent intervention indicated
Alkaline phosphatase	>ULN – 3.0×ULN	>3.0 – 5.0×ULN	>5.0 – 20.0×ULN	>20.0×ULN
ALT	>ULN – 3.0×ULN	>3.0 – 5.0×ULN	>5.0 – 20.0×ULN	>20.0×ULN
AST	>ULN – 3.0×ULN	>3.0 – 5.0×ULN	>5.0 – 20.0×ULN	>20.0×ULN
Bilirubin (hyperbilirubinemia)	>ULN – 1.5×ULN	>1.5 – 3.0×ULN	>3.0 – 10.0×ULN	>10.0×ULN
Calcium, serum-low (hypocalcemia)	<LLN – 8.0 mg/dL <LLN – 2.0 mmol/L	<8.0 – 7.0 mg/dL <2.0 – 1.75 mmol/L	<7.0 – 6.0 mg/dL <1.75 – 1.5 mmol/L	<6.0 mg/dL <1.5 mmol/L
Calcium, serum-high (hypercalcemia)	>ULN – 11.5 mg/dL >ULN – 2.9 mmol/L	>11.5 – 12.5 mg/dL >2.9 – 3.1 mmol/L	>12.5 – 13.5 mg/dL >3.1 – 3.4 mmol/L	>13.5 mg/dL >3.4 mmol/L
Cholesterol, serum-high (hypercholesterolemia)	>ULN – 300 mg/dL >ULN – 7.75 mmol/L	>300 – 400 mg/dL >7.75 – 10.34 mmol/L	>400 – 500 mg/dL >10.34 – 12.92 mmol/L	>500 mg/dL >12.92 mmol/L
Creatinine	>ULN – 1.5×ULN	>1.5 – 3.0×ULN	>3.0 – 6.0×ULN	>6.0×ULN
GGT (γ-glutamyl transpeptidase)	>ULN – 3.0×ULN	>3.0 – 5.0×ULN	>5.0 – 20.0×ULN	>20.0×ULN
Glucose, serum-high (hyperglycemia)	Fasting glucose value: >ULN – 160 mg/dL >ULN – 8.9 mmol/L	Fasting glucose value: >160 – 250 mg/dL >8.9 – 13.9 mmol/L	>250 – 500 mg/dL; >13.9 – 27.8 mmol/L; hospitalization indicated	>500 mg/dL; >27.8 mmol/L; life-threatening

Sponsor's Grading for Laboratory Values

	Grade 1	Grade 2	Grade 3	Grade 4
				consequences
Glucose, serum-low (hypoglycemia)	<LLN – 55 mg/dL <LLN – 3.0 mmol/L	<55 – 40 mg/dL <3.0 – 2.2 mmol/L	<40 – 30 mg/dL <2.2 – 1.7 mmol/L	<30 mg/dL <1.7 mmol/L life-threatening consequences; seizures
Phosphate, serum-low (hypophosphatemia)	<LLN – 2.5 mg/dL <LLN – 0.8 mmol/L	<2.5 – 2.0 mg/dL <0.8 – 0.6 mmol/L	<2.0 – 1.0 mg/dL <0.6 – 0.3 mmol/L	<1.0 mg/dL <0.3 mmol/L life-threatening consequences
Potassium, serum-high (hyperkalemia)	>ULN – 5.5 mmol/L	>5.5 – 6.0 mmol/L	>6.0 – 7.0 mmol/L hospitalization indicated	>7.0 mmol/L life-threatening consequences
Potassium, serum-low (hypokalemia)	<LLN – 3.0 mmol/L	<LLN – 3.0 mmol/L; symptomatic; intervention indicated	<3.0 – 2.5 mmol/L hospitalization indicated	<2.5 mmol/L life-threatening consequences
Sodium, serum-high (hyponatremia)	>ULN – 150 mmol/L	>150 – 155 mmol/L	>155 – 160 mmol/L hospitalization indicated	>160 mmol/L life-threatening consequences
Sodium, serum-low (hyponatremia)	<LLN – 130 mmol/L	N/A	<130 – 120 mmol/L	<120 mmol/L life-threatening consequences
Triglyceride, serum-high (hypertriglyceridemia)	150 – 300 mg/dL 1.71 – 3.42 mmol/L	>300 – 500 mg/dL >3.42 – 5.7 mmol/L	>500 – 1000 mg/dL >5.7 – 11.4 mmol/L	>1000 mg/dL >11.4 mmol/L life-threatening consequences
Uric acid, serum-high (hyperuricemia)	>ULN – 10 mg/dL ≤0.59 mmol/L without physiologic consequences	N/A	>ULN – 10 mg/dL ≤0.59 mmol/L with physiologic consequences	>10 mg/dL >0.59 mmol/L life-threatening consequences

Based on Common Terminology Criteria for Adverse events (CTCAE) Version 4.0. Published: 28 May 2009 (v4.03: 14 Jun, 2010).

ALT = alanine aminotransferase (serum glutamic pyruvic transaminase), AST = aspartate aminotransferase (serum glutamic oxaloacetic transaminase), GGT = γ -glutamyl transpeptidase, , LLN = lower limit of normal, N/A = not applicable, ULN = upper limit of normal, WBC = white blood cell.

